^A contrast enhanced MRI scan may be needed depending on AFP levels (see section 11.2) *Indeterminate lesions will be those that are not definitely HCC and not definitely benign (LI-RADS 3 or LI-RADS 4). The local HCC multidisciplinary team will determine how these are followed up (assessment with alternative imaging modality, interval contrast enhanced scan, biopsy or another follow-up strategy). For the analysis of sensitivity and specificity that will be conducted over the 30 months of follow-up, cases where surveillance tests identified indeterminate lesions, will be counted as true

positives if the lesion progresses to HCC by the end of follow-up and as false positive if they remain indeterminate or are subsequently classed as definitely benign. For the analysis that will be conducted for each surveillance round, the number of indeterminate lesions identified by nceMRI and / or USS will be recorded.

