9.8.1. Description of comparator(s)

The comparator will be the diagnosis of hepatocellular carcinoma based on the typical features on contrast enhanced MRI or CT or histological diagnosis (biopsy or resection) or a consensus diagnosis of HCC as determined by the local MDT will be accepted as a diagnosis of HCC.

On study contrast enhanced MRI scans

For cases where a contrast enhanced MR is done following a positive surveillance test (on study ceMRI), lesions classified as LI-RADS 1 or 2 will be regarded as negative for HCC and lesions classified as LI-RADS 5 will be regarded as positive for HCC. Lesions classified as LI-RADS 3 or 4 will be regarded as indeterminate and will be followed up according to the local clinical routine. If LI-RADS 3 or 4 are designated as HCC by the local MDT, or they are proven to be HCC on biopsy, or they progress to LI-RADS 5 within the 30 months of follow-up then they will be defined as HCC for the analysis relating to the whole 30 month period of surveillance. In cases where LI-RADS 3 or 4 lesions remain under follow-up at the end of the 30 months follow-up without a clear classification as HCC or benign, or where they have been histologically proven to be benign, then they will be classified as negative for HCC for the purposes of the analysis. The classification of lesions at on-study ceMRI scans is shown below in Figure 2. The follow-up of LI-RADS 3 and 4 lesions in this situation will finish at the timepoint that visit 6 was due or at an earlier time point if a definitive classification is reached before then.

Figure 2: Flowchart for the classification of lesions detected on contrast enhanced MRI performed during the study following a positive surveillance test. In cases where lesions are determined as negative within the 30-month surveillance period, participants will re-enter the AMULET surveillance schedule until they complete the study. Where a positive for HCC diagnosis is made, participants will end their participation, will undergo no further surveillance and will be managed according to the recommendations of the local MDT. Participants with LI-RADS 3 or 4 lesions who are undergoing interval contrast enhanced imaging as recommended by the local MDT will be suspended from participation in AMULET.

End of Study contrast enhanced MRI scan

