Participants that complete all 6 rounds of surveillance without a positive surveillance test and without HCC will undergo a contrast enhanced MRI at the end of the study (end of study ceMRI). The diagnostic allocation schedule will be modified for these scans as there will be no opportunity to follow-up LI-RADS 3 and 4 lesions. In these scans LI-RADS 1, 2 and 3 will be classed as not HCC and LI-RADS 4 and 5 lesions will be classed as HCC.

Follow-up for indeterminate lesions beyond 30 months

To enable potential future research, participant consent will be sought to allow follow-up through medical records or through data provided from NHS England, the NHS Central Register for Scotland and other patient registries for up to 10 years after their study participation is completed. This is to allow for collection of data relating to lesions that are still indeterminate at the end of 30 months surveillance period and to evaluate if those without HCC at the end of the study still go on to develop HCC. To facilitate this follow-up, personal identifiable information will be collected and stored centrally with participants' permissions.

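### A LI-RADS 4 lesion unresolved at month 30 is negative for HCC if a surveillance test flagged it but HCC if neither did, and the stated reason fails for lesions first flagged at visit 6

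*Protocol*

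**What the plan says.** Section 9.8.1 of the protocol holds two classification rules for contrast-enhanced MRI (ceMRI).

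- **On-study rule.** Its scope is "For cases where a contrast enhanced MR is done following a positive surveillance test (on study ceMRI"). LI-RADS 3 and 4 are indeterminate and followed locally. They become HCC if the MDT designates them so, if biopsy proves it, "or they progress to LI-RADS 5 within the 30 months of follow-up then they will be defined as HCC". Otherwise: "In cases where LI-RADS 3 or 4 lesions remain under follow-up at the end of the 30 months follow-up" without a clear classification, "then they will be classified as negative for HCC for the purposes of the analysis". On timing: "The follow-up of LI-RADS 3 and 4 lesions in this situation will finish at the timepoint that visit 6 was due", or earlier if the lesion is settled sooner.
- **End-of-study rule.** Its scope is: "Participants that complete all 6 rounds of surveillance without a positive surveillance test and without HCC will undergo a contrast enhanced MRI". Here LI-RADS 1 to 3 are not HCC, but "LI-RADS 4 and 5 lesions will be classed as HCC". The reason given for the change is that these lesions can no longer be followed.

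The footnote to Figure 1 in section 7 counts surveillance-detected indeterminate lesions "as false positive if they remain indeterminate or are subsequently classed as definitely benign". Section 11.2 assigns true and false negatives at the end-of-study ceMRI and compares sensitivity and specificity by McNemar's test. Section 9.10 and Appendix A give every participant a ceMRI at visit 6.

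**The concern.** A reference standard should not depend on the index tests it is used to judge. Here the cut-point for disease moves from LI-RADS 5 to LI-RADS 4 according to whether a surveillance test was positive. The label feeds the 30-month sensitivity and specificity in the primary objective. About 50 HCCs are planned, so a handful of reclassified lesions can move the headline sensitivities by several points. Where only one test flags the lesion, the rule sets the result against the test that saw it and credits the test that did not.

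**Working it through.** **Step 1: the rules applied to one finding.** Take three participants whose visit 6 ceMRI shows the same LI-RADS 4 lesion. None was flagged before, and neither MDT nor biopsy has settled the lesion.

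| Surveillance at visit 6 | Rule that applies | Reference status | nceMRI | USS |
|---|---|---|---|---|
| Both tests positive | On-study | Negative | FP | FP |
| nceMRI positive only | On-study | Negative | FP | TN |
| Neither positive | End-of-study | HCC | FN | FN |

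All three have the same scan result and no interval follow-up, because follow-up of flagged lesions also closes when visit 6 is due. Only the index-test result differs. LI-RADS 3 raises no conflict: if unresolved, it is not HCC under either rule.

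**Step 2: illustration of size.** No figure in the protocol depends on this point, so there is none to reproduce. Inputs from section 11.3: 50 HCCs, 250 controls (the lower end of its range), specificity 80% for nceMRI and 90% for USS, and sensitivity 80% and 50%, both within its planning ranges. Assumed: the number *k* of LI-RADS 4 lesions, which the protocol does not give. The *k* lesions are added to the 50 HCCs and 250 controls.

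Base counts: nceMRI detects 0.80 × 50 = 40 HCCs and USS 0.50 × 50 = 25. True negatives are 0.80 × 250 = 200 for nceMRI and 0.90 × 250 = 225 for USS.

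(a) *k* lesions missed by both tests and classed as HCC (current rule): sensitivity is 40/(50 + k) for nceMRI and 25/(50 + k) for USS.

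| k | nceMRI | USS | Difference |
|---|---|---|---|
| 0 | 80.0% | 50.0% | 30.0 points |
| 3 | 40/53 = 75.5% | 25/53 = 47.2% | 28.3 |
| 5 | 40/55 = 72.7% | 25/55 = 45.5% | 27.3 |
| 10 | 40/60 = 66.7% | 25/60 = 41.7% | 25.0 |

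Classed as negative, these lesions leave sensitivity at 80% and 50%. McNemar's statistic, (b − c)²/(b + c), uses only the discordant counts b and c. Lesions missed by both are concordant, so the sensitivity test is unchanged. The estimates and their difference are not.

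(b) *k* unresolved lesions flagged by nceMRI only.

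| k | Current rule (negative): specificity nceMRI / USS | If classed as HCC: sensitivity nceMRI / USS |
|---|---|---|
| 5 | 200/255 = 78.4% / 230/255 = 90.2% | 45/55 = 81.8% / 25/55 = 45.5% |
| 10 | 200/260 = 76.9% / 235/260 = 90.4% | 50/60 = 83.3% / 25/60 = 41.7% |

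Under the current rule these lesions are discordant pairs against nceMRI for specificity. Classed as HCC, they would be discordant pairs in its favour for sensitivity.

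**The case against.** The best defence is that the two groups differ. A lesion flagged at visits 1 to 5 and left unresolved has been followed without reaching LI-RADS 5, whereas an unflagged lesion is seen once, on the last scan, and is not shown to persist. Treating a followed, non-progressing lesion differently from a single observation is a reasoned choice. That part stands. It does not reach lesions first flagged at visit 6, which are also seen once.

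Three stronger readings are tempting, and the protocol does not support them.

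- *A lesion flagged at visit 6 is automatically a false positive, or detection can only cost a test.* A flagged lesion becomes HCC, and the flagging test a true positive, by MDT designation, biopsy or progression. At visit 6 the first two remain possible in principle.
- *A LI-RADS 4 lesion counts against the tests either way.* When one test alone flags it, the other is credited with a true negative.
- *Sensitivity and specificity of both tests are biased down.* Direction depends on what the lesions are. If unflagged LI-RADS 4 lesions are HCC, those false negatives are correct. If stable flagged lesions are benign, those false positives are correct. The protocol gives no HCC rate for LI-RADS 4.

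The counts in the illustration are also open to challenge. If nceMRI detected LI-RADS 4 lesions at the assumed 80%, at most 20% could be missed by both tests, so 3 to 10 such lesions would imply at least 15 to 50 in all (3/0.2 and 10/0.2). Fewer lesions, or better detection, means a smaller effect.

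**Conclusion.** The point holds in this form: for a LI-RADS 4 lesion unresolved at month 30, the reference label depends on the surveillance result, and identical visit 6 findings can receive opposite labels in the primary accuracy analysis. The stated reason does not cover that case. This is wrong as written and not a detail left to the SAP, because section 9.8.1 fixes both rules itself.

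The size is unknown. With 3 to 10 lesions missed by both tests, the choice of label moves nceMRI sensitivity by 4.5 to 13.3 points (80% less 75.5% to 66.7%) and USS sensitivity by 2.8 to 8.3 points (50% less 47.2% to 41.7%). It leaves the McNemar test of sensitivity unchanged. With 5 to 10 lesions flagged by nceMRI only, the current rule costs nceMRI 1.6 to 3.1 points of specificity (80% less 78.4% to 76.9%). These figures rest on assumed lesion counts and section 11.3 planning values. They show how far the choice of label can matter and do not estimate a bias in a known direction.

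**What to change.** The change concerns analysis classification only, not how any lesion is managed.

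1. At minimum, classify every visit 6 ceMRI with the same table, whatever the surveillance tests showed.
2. Preferably, apply one rule to all LI-RADS 4 lesions unresolved at the month-30 cut-off. Word it to cover two cases that neither present rule reaches: a LI-RADS 4 lesion on a ceMRI triggered by AFP, and one on the visit 6 ceMRI of a participant whose earlier positive test was resolved as false.
3. Report the primary accuracy results also with all unresolved LI-RADS 4 lesions as HCC and with all as not HCC, if the SAP does not already provide for this.

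Set the rule before outcomes are known, since one chosen later could be seen as favouring a test. The registry follow-up of indeterminate lesions already foreseen in section 9.8.1 can later check the choice. The cost is wording in section 9.8.1, Figures 1 and 2 and the SAP, plus two extra tabulations. No scans are added.

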9.8.2. Description of study procedure(s)

Collection of Demographics and Medical History

A member of the study team will access the medical notes of the participant to obtain information about the individual's demographics, medical history, anthropological measurements (height, weight and resulting BMI) and previous clinical imaging data.

Participant questionnaires

Participants will be asked to complete paper copies of the EQ-5D-5L questionnaire and Hospital Anxiety and Depression Scale (HADS) at each research visit, and a study specific participant experience questionnaire relating to USS and nceMRI at the baseline visit and visit 5. Data will be transferred from the completed paper copies to the study electronic case record form by the site study investigators.

Ultrasound scan

USS reporting for the imaging findings

Ultrasound scans are performed as part of the participant's routine clinical care. Surveillance USS findings will be interpreted and reported by appropriately trained and experienced sonographers or radiologists at each site, who will receive training in study specific assessments and documentation, including the blinding process. Each USS episode will have a findings category score assigned using the US LI-RADS³⁷ reporting system (US1-negative; US2 subthreshold; US3 positive)."US1- negative" examinations will be those where no suspicious observations are noted, or where there are only definite benign observations. "US3 -positive" examinations will be those with an observation ≥10mm in diameter

that is not definitely benign, including areas of parenchymal distortion or new thrombus in the portal vein or hepatic vein. "US2 subthreshold" examinations will be those with observations <10mm in diameter that are not definitely benign.

"US1- negative" will be designated as negative examinations for the purposes of our study. Participants will return for 6 monthly surveillance after an "US1-negative" examination.

"US3 positive" will be designated as positive examinations for the purposes of our study and will be followed up by a full contrast enhanced MRI scan.

"US2 subthreshold" will be classed as negative in our study and handled in the same way as "US1negative". The LI-RADS recommendation is that these cases can be followed up with repeat ultrasound in 3-6 months and since our study protocol will include 6 monthly scans, our scanning schedule is within this recommendation. Furthermore, data suggests that sub-threshold lesions are unlikely to progress to HCC³⁸. Discretion will be allowed if the clinical teams decide to follow a more frequent scanning schedule (e.g. after 3 or 4 months).

USS reporting for the imaging quality The US LI-RADS visualisation score will be used to describe the quality of the USS examination as:

VIS A: no or minimal limitations

VIS B: moderate limitations

VIS C: severe limitations

Non-contrast enhanced Magnetic Resonance Imaging

Safety screening and participant safety during the scanning sessions

Contraindications to magnetic resonance imaging will be excluded by use of the radiology departments screening forms. For this, trained radiology department staff will go through a safety questionnaire with the participant before scanning as per standard clinical practice. The MRI scanner consists of a large powerful magnet. Magnetic resonance imaging uses no ionising radiation. There are, however, potential hazards associated with MRI and the scanning of participants including the presence of surgical implants, participants' clothing, jewellery (such as body piercings), bodily habitus, or medical conditions. A comprehensive list of potential risks has been compiled, and the participant should be checked against this by the operator, prior to entering the controlled areas of the MRI scanners, according to local SOPs. During the actual scanning procedure, the scanner produces loud noises and facility procedures will be followed regarding hearing protection including the use of earplugs. Small mirrors that will allow participants to see out of the scanner and relieve feeling of claustrophobia may be used. During the scan, the participant will be able to communicate with the operator in the control room. In addition, they will be given a call button, which allows them to alert the operator at any time. People with a history of claustrophobia may be excluded from participation in the study if they are unable to tolerate MRI. All participants will still be introduced carefully to the scanner and allowed to leave at any stage, should they wish to do so. Once in the scanner, participants will be able to indicate immediately if they wish the scanning to cease by pressing a call button in their hands.

nceMRI: image acquisition

The nceMRI protocol includes three "core" nceMRI sequences (Table 1) to address the primary aim of assessing diagnostic accuracy of lesion recognition. These can be acquired within a 15-minute scan slot. Four additional nceMRI sequences (adding ~10 minutes of scan time) will be acquired with patient consent for the purpose of the mechanistic sub-study. To ensure widespread NHS utility, our protocol is scanner/vendor/field strength (1.5/3T) agnostic and has sufficient spatial resolution (~2-3 mm in-plane, 3-5 mm axial slices) to detect small HCCs (<2 cm) across the whole liver.

All recruiting sites will need to acquire and report on the core sequences for the presence or absence of a suspicious nodule. MRI scans will be performed with participants fasted for at least 4 hours. The quantitative mechanistic sequences will be acquired by centres with appropriate MR capabilities and will not require radiological reporting. **Table 1:** nceMRI protocol comprising core sequences for lesion recognition and mechanistic sequences to study the background "field effect".

MRI sequence	Scan Duration	Suspicious Lesion Recognition	Mechanistic Study
Core Sequences:			
 1 T₂-weighted (T2WI) A) Turbo-spin echo (TSE) echo time (TE) ~90 ms, fat suppressed (FS). B) FSE with no FS and long TE >120ms. 	3 min (6 x 15 s breath hold (BH))	Mild-moderately hyperintense. High T ₂ weighting to distinguish between cystic and solid lesions. Fat containing HCC : Isointense on T2WI FS. Iron containing HCC : Hypointense on T2WI.	Radiomics features of background liver for study of "field effects".
 2 T₁-weighted (T1WI) A) Dual gradient in-phase (IP)/out phase (OP) recalled echo (GRE). B) 3D Thrive with FS. 	1 min (2 x 15 s BH)	Hypointense in OP compared to IP due to fat sparing. Hypointense in IP due to iron deposition. Thrive hypointense in fat sparing. Nodule-in-nodule/mosaic architecture.	Radiomics features of background liver for study of "field effects".
3 Diffusion weighted (DWI) DWI with 4 b-values from 0- 800 s/mm ² . (Spans range in MAGNUS-HCC and MIRACLE-HCC trials.)	4 min (Free breathing)	Hyperintense on high b-value. ADC of lesion similar or hypointense due to diffusion restriction. Fat containing HCC : Isointense on DWI FS.	"Field effects" in ADC.
Quantitative Mechanistic Seque	nces:		
4 Diffusion weighted (DWI) Protocols as collected in 3 above but with additional DWI b-values for IVIM	4 min (Free breathing)	Hyperintense on high b-value. ADC of lesion similar or hypointense due to diffusion restriction. Fat containing HCC : Isointense on DWI FS.	"Field effects" in IVIM maps of restricted diffusion and vascularity.
6 3D multi-echo DIXON Quantitative 6 echo DIXON with short echo times (1–6 ms).	30 s (1 x 16 s BH)	IP and OP as for 2, as well as fat (F) and water (W) images. Fat fraction (PDFF) and R ₂ * maps to detect fat sparing lesions.	"Field effects" in PDFF and R ₂ * maps.
7 3D R ₂ * mapping High resolution R ₂ * mapping with 12 echoes with longer echo times (1– 18 ms).	1 min (2 x 16 s BH)	R ₂ * hyperintense for iron sparing lesions.	"Field effects" in R_2^* map.
8 3D T_1 mapping Variable flip angle T_1 , plus B_1 and B_0 mapping.	4 min (6 x 15 s BH)	T ₁ mild-moderately hyperintense.	"Field effects" in T_1 map.

nceMRI: reporting for the imaging findings

nceMRI will be evaluated by board-certified abdominal radiologists at each site using a standardised proforma. On nceMRI, a suspicious nodule is defined as a solid newly appearing nodule ≥ 1 cm that is not definitely benign. Diffuse infiltrative lesions with or without suspected tumour in vein are also considered suspicious. Simple cysts, haemangiomas, and lesions previously diagnosed as benign lesions are not considered suspicious, irrespective of the size.

nceMRI: reporting for the quality of the scans

Automated quantitative quality assurance (QA) of nceMRI in terms of image signal-to-noise ratio (SNR) measures will be performed and these results will be stored on the XNAT platform that will be used for imaging data management. Furthermore, nceMRI scans will be reported locally using a standardised proforma that will be developed based on other multicentre studies that have investigated implementation of MRI (e.g. STREAMLINE-C³⁹ and STREAMLINE-L⁴⁰).

Contrast enhanced magnetic resonance imaging

In addition to the checks for the safety of having an MRI scan (which will be the same as for the nceMRI scan) there will be added check for the safety of receiving intravenous gadolinium contrast. Gadolinium contrast is contraindicated in people with eGFR <30 ml/min/1.73m². Estimated GFR will therefore be checked prior to inclusion in the study (see exclusion criteria) and before each ceMRI procedure. For the ceMRI an intravenous cannula will be inserted into the participants arm by a radiographer or other appropriately trained person. Scans will be acquired before and after the administration of an intravenous contrast agent. Scans will be reported by study radiologists at each site using a standardised proforma including LI-RADS classification.

9.9. Baseline Assessments

The baseline visit (visit 1) will last around 120 minutes and will take place at NHS Hospital Trusts and academic centres. This visit will ideally take place on a single day but may take place on two separate days, with the first imaging scan and data collection taking place up to 28 days prior to the second imaging scan (see also section 9.7).

A member of the study team will check eligibility of the participant and will answer any further questions a participant might have. The participant is fully enrolled into the study if eligibility criteria are met and written informed consent has been obtained. On enrolment into AMULET, each patient will be assigned a unique study number. All clinical and imaging data will be recorded against that number. Once written informed consent has been obtained, participants will receive the following assessments/procedures (details can be found above):

- Collection of Demographics and Medical History (duration 10 minutes)
- Physical Examination (recording of height and weight) (duration 5 minutes)
- Completion of MRI safety check (5 minutes)
- Clinical care USS (20 minutes)
- NceMRI (20 minutes)
- Completion of EQ-5D-5L and HADS questionnaires at the beginning of the study visit (30 minutes)
- Acceptability of MRI and USS as surveillance test questionnaire (to be completed immediately after the relevant scan; 30 minutes)

